#### 7.5.2 Secondary Endpoint Analyses

##### 1. **Successful Procedural Revascularization (final mTICI $\geq 2b$ )**

The number and percentage of subjects with a final (end of procedure) mTICI score  $\geq 2b$  will be summarized.

Subjects with a missing mTICI score (from the imaging core lab) at the end of procedure will be imputed with the non-missing mTICI score from the last procedural pass (e.g., pass 1 to 10) from the imaging core lab if there were no post mechanical thrombectomy interventions and no intra-arterial thrombolytic agent performed after the final procedural pass.

##### 2. **Excellent Procedural Revascularization (final mTICI $\geq 2c$ )**

The number and percentage of subjects with a final (end of procedure) mTICI score  $\geq 2c$  will be summarized.

Subjects with a missing mTICI score (from the imaging core lab) at the end of procedure will be imputed with the non-missing mTICI score from the last procedural pass (e.g., pass 1 to 10) from the imaging core lab if there were no post mechanical thrombectomy interventions and no intra-arterial thrombolytic agent performed after the final procedural pass.

##### 3. **First Pass Revascularization using NIMBUS (mTICI $\geq 2b$ )**

The number and percentage of subjects with an mTICI score  $\geq 2b$  following the first pass of NIMBUS will be summarized. Subjects with a missing mTICI score (from the imaging core lab) for the first pass using Nimbus, will be imputed with the final (end of procedure) mTICI score from the imaging core lab if the first pass using Nimbus is the last procedural pass, there were no post mechanical thrombectomy interventions and no intra-arterial thrombolytic agent were performed after the first Nimbus pass.

#### **4. Occurrence of Embolization to a New Territory (ENT)**

The number and percentage of subjects with ENT following the final pass of NIMBUS will be summarized.

#### **5. Symptomatic Intracerebral Hemorrhage (sICH) at 24 hours specified according to the Heidelberg Bleeding Classification (HBC).**

sICH is defined as a new intracranial hemorrhage as detected by brain imaging, measured at 24 hours post-procedure. The number and percentage of subjects with sICH up to 24 hours post-procedure as assessed by HBC will be summarized.

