#### **5.3 Independent Core Laboratory for Image Evaluation**

All imaging collected will be SOC, no additional imaging will be requested for this study. Imaging should include full A-P lateral images for the start and the end of each procedural pass. An independent radiographic core laboratory shall be utilized to provide an unbiased and standardized assessment of all collected imaging. All subject protected health information will be removed before an image is uploaded and evaluated. The core lab assessor will be blinded to subjects' previous medical history. Each angiogram will be read independently by experienced Imaging Core Lab neuro-interventionalists.

The objective of the Imaging Core Lab will be to:

- Review all angiograms obtained
- Provide an unbiased assessment of the rate of revascularization defined by mTICI scores based on angiographic imaging from the study sites
- Evaluate CT/MRI examinations to detect and assess hemorrhages.

This study will be collecting the following imaging data to be assessed by Imaging Core Lab:

- Baseline - CT/ MR imaging
  - Infarct volume
  - Clot location
  - Clot length
  - Clot radiodensity on CT / Susceptibility Vessel Sign (SVS) on MRI
- Procedural Angiography
  - mTICI score for every pass
  - Clot location for every pass (proximal face of clot)
  - Emboli to new territories
- Post Procedure - CT/ MR imaging
  - Intracranial Hemorrhage

Hemorrhages will be classified according to the following categories [36]:

- HI 1 – Scattered small petechiae, no mass effect
- HI 2 – Confluent petechiae, no mass effect
- PH1 – Hematoma within infarcted tissue, occupying <30%, no substantive mass effect
- PH2 – Hematoma occupying 30% or more of the infarcted tissue, with obvious mass effect
- RIH – Parenchymal hematoma remote from infarcted brain tissue
- IVH – Intraventricular Hemorrhage
- SAH – Subarachnoid Hemorrhage
- SDH – Sub Dural Hemorrhage

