# 7 SAFETY ASSESSMENT

## 7.1 Specific Safety Parameters

For purposes of obtaining long-term safety surveillance in this study, **AEs will be reported and recorded (via eCRF) if any of the following apply:**

- The event is neurological in nature
- The event is a serious adverse event (SAE)
- Causality is related to:
  - The device, or
  - The procedure, or
  - If causality is unknown

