## 3 Interval Windows

Study reports will be summarized by analysis visit as defined in the protocol:

- 24 Hours post-procedure ( $\pm 8$  hours)
- 90-day follow-up ( $\pm 14$  days)

The study schedule is to be adhered to as closely as possible for all subjects. Measurements outside the interval windows will be treated as missing. In the case of repeated measurements taken at the same visit, the most recent non-missing measurement will be used unless specified otherwise.

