## 7 Analyses to be Conducted

### 7.1 General Conventions

Descriptive summary statistics will be presented for all endpoints. The number and percentage of subjects will be summarized for categorical variables. Unless specified otherwise, percentages will be based on subjects with non-missing values. Descriptive statistics for continuous variables will include the number of subjects, mean, standard deviation, median, first quartile (Q1), third quartile (Q3), minimum and maximum. All statistical analyses will be performed using SAS® Studio, Version 9.4 or later.

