#### **7.5 Primary and Secondary Endpoint Analyses**

mTICI scores and embolization to a new territory (ENT) will be summarized using the assessments from the independent core lab. Unless instructed otherwise, missing values will be excluded from the analysis. Exact CIs will be conducted around the percentage, unless instructed otherwise.

All-cause mortality and mRS  $\leq 2$  at 90 days will be analyzed using mITT and mRS analysis sets, all other endpoints will be analyzed using the mITT analysis set.

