#### **7. Modified Rankin Scale (mRS) ≤ 2 at 90 days.**

The number and percentage of subjects with mRS scores ≤ 2 at 90 days (76 days or above) will be summarized using the mRS analysis set. Subjects with missing mRS scores due to all-cause mortality are considered to have an mRS score of 6 in the analysis. Subjects with missing data due to reasons other than all-cause mortality will be excluded from analysis. Subjects with mRS scores outside or didn't reach the 90-day window, due to reasons other than mortality, will be listed together with their mTICI scores at end of procedure and after final pass of NIMBUS.

In addition to the primary analysis using the mRS analysis set, the same analysis will be repeated using the mITT analysis set.

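### Does counting sICH up to 24 hours lose bleeds imaged only before 16 hours or first seen at 24 to 32 hours?

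*SAP*

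**What the plan says.** SAP 7.5.2 item 5 has two sentences on sICH. The first fixes the measurement: "sICH is defined as a new intracranial hemorrhage as detected by brain imaging, measured at 24 hours post-procedure". The second fixes the count: "The number and percentage of subjects with sICH up to 24 hours post-procedure as assessed by HBC will be summarized". Protocol 3.2.2 and 9.7.4.2 refer only to sICH at 24 hours, and SAP 7.11 does not list the new wording as a change.

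Three general rules sit around this item:

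- SAP 3 defines the 24-hour analysis visit as 24 hours plus or minus 8 and adds: "Measurements outside the interval windows will be treated as missing".
- SAP 7.1: "Unless specified otherwise, percentages will be based on subjects with non-missing values".
- SAP 7.5: "Unless instructed otherwise, missing values will be excluded from the analysis".

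The protocol's schedule of assessments makes imaging at the 24-hour visit a required item. Protocol 5.3 provides that "An independent radiographic core laboratory shall be utilized to provide an unbiased and standardized assessment of all collected imaging". Protocol Table 3 gives the Heidelberg definition. It needs a new hemorrhage on imaging, and it judges worsening on the NIHSS against the state just before deterioration, not against a scheduled visit.

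**The concern.** The two sentences of item 5 use different time bases, and neither gives hour limits. An analyst who applied every rule at its strictest could lose two kinds of event:

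- **Early bleed.** A patient deteriorates soon after the procedure, is scanned before 16 hours, and has no later scan, for instance because of death. Under SAP 3 that scan is out of window and so missing. Under SAP 7.1 and 7.5 the subject then leaves both numerator and denominator. Such a loss would be informative, because deterioration is what prompts the early scan.
- **Late bleed within the visit.** A hemorrhage is first seen on a compliant scan at, say, 30 hours. A strict 24-hour clock limit would record a non-event.

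The SAP does write a rule of this kind elsewhere. For the 90-day Rankin score it says: "Subjects with missing mRS scores due to all-cause mortality are considered to have an mRS score of 6 in the analysis". Item 5 has no counterpart for a subject who dies before the 24-hour scan. At stake is a safety rate in a study of about 50 subjects, where a single event is visible in the percentage.

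**Working it through.** **The plan's own figures.** The plan states no expected rate or precision for sICH. Its only precision figure is for the primary endpoint: 1.96 × √(0.86 × 0.14 / 45) = 10.14%, which matches the stated 10.1%. It does not depend on the sICH rule.

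**The window.** 24 − 8 = 16 hours and 24 + 8 = 32 hours.

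**The readings side by side.**

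| Bleed | Procedure through 24-hour visit (0–32 h) | Clock limit only (0–24 h) | SAP 3 window only (16–32 h) | Both limits (16–24 h) |
|---|---|---|---|---|
| Imaged only before 16 h | counted | counted | missing | missing |
| Seen at 16–24 h | counted | counted | counted | counted |
| First seen at 24–32 h | counted | non-event | counted | non-event |

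Each single rule loses one kind of case and keeps the other. Both are lost only if the two limits are stacked into 16 to 24 hours, which no sentence in either document asks for.

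**Which reading the text supports.** SAP 3 labels the visit as 24 hours post-procedure with its 8-hour tolerance, and item 5 uses the same label. Counting up to that visit therefore runs to its end, so a 30-hour scan is inside. The SAP's wording also turns the protocol's point-in-time rate into a cumulative one, and that takes in earlier bleeds. The exclusion rules in SAP 7.1 and 7.5 give way where something else is specified, and a cumulative count is reasonably such a specification. The missing-value sentence in SAP 3 has no such clause, but it concerns measurements assigned to visits, whereas the Heidelberg definition is built on an event.

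**Size of one misclassified subject.** Take N = 50 and k true events. Protocol 1.2.2 quotes sICH rates of 0 to 9.3% from other studies, so the expected number is 0 to 0.093 × 50 = 4.65.

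- An early event dropped from numerator and denominator: k/50 − (k − 1)/49 = (50 − k)/2450. This is 2.00 points for k = 1, 1.92 for k = 3 and 1.84 for k = 5.
- A late event counted as a non-event: 1/50 = 2.00 points (1/45 = 2.2 if N = 45).
- An event-free subject dropped because the only scan was out of window: k/49 − k/50 = k/2450. This raises the rate by 0.12 points for k = 3 (6.0% to 6.1%) and 0.20 for k = 5.

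The strict window rule can therefore move the rate either way, although a lost event weighs far more than a lost non-event.

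**Illustration with assumed counts.** Suppose four events among 50 subjects: one imaged only before 16 hours, two seen at 16 to 24 hours, and one first seen at 24 to 32 hours. Intervals are exact 95%.

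| Reading | Count | Rate | Interval |
|---|---|---|---|
| 0–32 h | 4/50 | 8.0% | 2.2–19.2 |
| 0–24 h | 3/50 | 6.0% | 1.3–16.5 |
| 16–32 h, early scan missing | 3/49 | 6.1% | 1.3–16.9 |
| 16–24 h, early scan missing | 2/49 | 4.1% | 0.5–14.0 |

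The example places one case in each gap on purpose. Even so, the intervals overlap over most of their length.

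**The case for a change.** The strongest case for a change is that the SAP writes exceptions where it wants them. It widens the window for the 90-day Rankin score to day 76 and beyond, scores death as 6, and says in 7.11 that other 90-day endpoints are not tied to the visit window. sICH gets no such sentence. Protocol 6.6 defines unscheduled assessments only from discharge, so an in-hospital scan before 16 hours has no named visit, and a programmer working by rote might apply SAP 3 to it. Nor do the adverse event tables repair the rate: SAP 7.6 reports by MedDRA term, not by the Heidelberg classification.

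The silence is real, and the adverse event tables are only a partial safeguard. They do mean that the event is not lost from the report. Protocol 7.1 requires an adverse event to be recorded when "The event is neurological in nature", or when it is serious.

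The comparison with the Rankin score is weaker. That scale has a category for death. A subject who dies unscanned cannot be classified under a definition that requires a hemorrhage on imaging, and the death is counted in the mortality endpoint.

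A rewritten rule also has its own traps. If any scan between the procedure and 32 hours qualified a subject for the denominator, a single negative scan shortly after the procedure would count as event-free through 32 hours, which could understate the rate.

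**Conclusion.** No change to the plan follows. Item 5 leaves its counting period unwritten, but the reading that fits the SAP's own visit label and its cumulative wording, from the procedure through the end of the 24-hour visit, loses neither kind of case. An early-only bleed is lost only if the general rule in SAP 3 is allowed to override item 5. A bleed first seen at 24 to 32 hours is lost only under a strict clock limit that sits badly with the visit definition.

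Each lost event would cost about 2 percentage points at N = 50. The number at risk cannot be derived from the documents. It is likely very small, because the 24-hour scan is required, an early bleed may still show on it, and all collected imaging goes to the core laboratory. SAP 4 plans no hypothesis tests and offers the intervals only to convey precision. No significance level, power or sample size depends on the point.

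This conclusion assumes that the analysts count cumulatively through the visit. All event counts used above are assumptions.

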#### **6. 90 Day All-Cause Mortality.**

Kaplan-Meier analysis (product limit estimates) will be used to estimate all-cause mortality rate using mITT analysis set. All-cause mortality is defined as the event; and the date of mortality is considered as the date of event. Subjects without events will be censored at the date of last contact (e.g. date of study completion or early discontinuation). Deaths beyond 90 days will be listed.

Kaplan-Meier event (failure) rate and associated two-sided 95% CIs using log-log transformation will be reported, the estimate of standard error will be computed using Greenwood's formula.

In addition to the primary analysis using the mITT Analysis Set, the same analysis will be repeated using the mRS analysis set.

#### **7. Modified Rankin Scale (mRS) ≤ 2 at 90 days.**

The number and percentage of subjects with mRS scores ≤ 2 at 90 days (76 days or above) will be summarized using the mRS analysis set. Subjects with missing mRS scores due to all-cause mortality are considered to have an mRS score of 6 in the analysis. Subjects with missing data due to reasons other than all-cause mortality will be excluded from analysis. Subjects with mRS scores outside or didn't reach the 90-day window, due to reasons other than mortality, will be listed together with their mTICI scores at end of procedure and after final pass of NIMBUS.

In addition to the primary analysis using the mRS analysis set, the same analysis will be repeated using the mITT analysis set.

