## SCHEDULE OF ASSESSMENTS

Table 1: Schedule of Assessments

Table Legend: X = Required; O = Optional, to be collected if performed during standard of care	Enrollment			Follow-up	
	Baseline	Procedure	Post-procedure 24hrs (+/- 8 hrs)	90 Day Follow-up (+/- 14 days)	Unscheduled 
Assessments					
ICF	X				
Eligibility Screening	X				
Demographics and Medical History	X				
IV t-PA administration	O				
Imaging 	X	X	X		O
NIH Stroke Scale (NIHSS)	X		X	O	O
Modified Rankin Scale (mRS)	X			X	O
Angiography 		X			
Review of Applicable Adverse Events (AE)		X	X	X	X
Clot Collection 		X			

(1) CT/MR Imaging and angiography will be sent to independent Imaging Core Lab for review.

(2) Due to the emergent nature of AIS, consent may be obtained after the procedure but up to 7 days post-procedure as permitted by the local regulations and EC.

(3) Per pass clot collection to be sent to Central Lab for processing.

(4) If more than one NIHSS was performed during this time period, select the worst (highest) value.

(5) To be evaluated by a qualified evaluator; pre-stroke mRS should reflect the subject's condition just prior to the stroke onset. For example, if the subject was hospitalized during stroke onset, the subject's reason for hospitalization should be taken into account when evaluating the subject's pre-stroke mRS.

(6) Assessments should be completed for unscheduled visits from the time of Discharge up to (but not including) the 90-day Follow-up, where imaging, NIHSS, or mRS is performed as part of stroke management care for the subject.

(7) The 90 day mRS must be performed by a qualified independent evaluator who is not part of the interventional treating team.

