#### 7.11 Changes from the Planned Analyses

- Analysis window mRS  $\leq 2$  at 90-day

Due to the potential impact of Covid-19, it is expected that there may be more late 90-day mRS assessments compared to the SAP-defined 90-day window of  $\pm 14$  than anticipated. In order to minimize the impact of out of 90-day window assessments, analyses on mRS endpoint will include all available assessments on or after 76 days. Analyses using the 90-day window of  $\pm 14$  days will be considered part of the sensitivity analyses (section 7.8).

Other study endpoints at 90 days (e.g., all-cause mortality at 90 days) are not impacted by the 90-day window as other endpoints are not restricted by the compliance of the 90-day visit.

End of Document

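### The main 90-day mRS analysis has no last day and an undated death rule that applies only to missing scores, so it can disagree with the 90-day mortality endpoint about the same subject

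*SAP*

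**What the plan says.** **Visit window.** Protocol Table 1 sets the visit as "90 Day Follow-up (+/- 14 days"), which is days 76 to 104. SAP section 3 repeats this window and adds: "Measurements outside the interval windows will be treated as missing".

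**mRS endpoint (SAP 7.5.2 item 7).** Scores of 2 or less "at 90 days (76 days or above) will be summarized using the mRS analysis set". On deaths: "Subjects with missing mRS scores due to all-cause mortality are considered to have an mRS score of 6 in the analysis". Scores missing for any other reason are left out. Subjects outside the 90-day window, or who never reached it, are listed unless the reason was death. The analysis is repeated in the mITT set.

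**Mortality endpoint (SAP 7.5.2 item 6).** This is a Kaplan-Meier rate at 90 days, with the rule: "Deaths beyond 90 days will be listed".

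**Explanation (SAP 7.11).** Because late visits were expected under Covid-19, "analyses on mRS endpoint will include all available assessments on or after 76 days". Analyses using ±14 "days will be considered part of the sensitivity analyses (section 7.8"). The same section says: "Other study endpoints at 90 days (e.g., all-cause mortality at 90 days) are not impacted by the 90-day window".

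**Sensitivity analysis (SAP 7.8).** The ±14-day version uses observed data without carrying scores forward. It does not say how deaths are scored.

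**Purpose.** Protocol 9.5 created the mRS Analysis Set to make the result more comparable with published 90-day mRS outcomes.

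**The concern.** Two endpoints carry the label 90 days but treat time differently. Mortality stops at day 90. The mRS rate starts at day 76 and does not stop, and its death rule depends on whether a score is missing rather than on when the subject died.

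This has two consequences. First, one subject can be reported as independent at 90 days and as dead by 90 days, or as mRS 6 at 90 days and not dead by 90 days. Second, the headline rate depends partly on how late a site made its assessment, in a set that exists for comparison with published 90-day figures. Section 3 adds a further conflict: read alone, it makes a score after day 104 missing, while item 7 counts it.

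**Working it through.** **Inputs.** The index procedure is Day 0 (SAP 7.1). The protocol window is 90 − 14 = day 76 to 90 + 14 = day 104. The main mRS analysis runs from day 76 with no end. The mortality cut-off is day 90.

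**The rules applied to hypothetical subjects.**

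| Subject | Item 7, main mRS | SAP 7.8, ±14 days | Item 6, mortality |
|---|---|---|---|
| A: no score from day 76, dies day 120 | 6, if death is taken as the reason the score is missing | not stated; 6 if item 7's rule carries over | not a death by day 90; listed |
| B: seen only on day 180, mRS 2 | independent | missing | no death |
| C: mRS 2 on day 78, dies day 85 | independent | independent | death |
| D: dies day 40 | 6 | 6 if the rule carries over | death |
| E: no score, dies day 97 | 6, on the same reading as A | not stated; 6 if the rule carries over | not a death by day 90; listed |
| F: mRS 2 on day 92, dies day 110 | independent | independent | not a death by day 90; listed |

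D and F are consistent. C is a direct contradiction on the stated rules. A and E conflict on a reading that the text allows but does not compel. B shows the effect of having no last day.

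**Can these subjects occur?** For C, protocol 6.6 collects unscheduled mRS scores up to the 90-day visit, and section 7.11 admits every score from day 76. Such a subject is still in follow-up, so a later death is captured. If the day-78 score were instead the final visit, participation might end there and the death might go unrecorded. For A and E, protocol 6.8 does not treat a subject as lost until the final visit, and protocol 7.3 collects events to the end of participation. An overdue subject can therefore still contribute a late death.

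**Size.** The only precision figure in the plan is for revascularization: 1.96 × √(0.86 × 0.14 / 45) = 0.1014, which reproduces the stated 10.1%. The plan gives no size, rate or precision for the mRS endpoint. A subject who changes between independent and not independent moves the rate by 1/n:

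- n = 45, the plan's evaluable number: 1/45 = 2.2 points
- n = 30 (assumed mRS set): 1/30 = 3.3 points
- n = 20 (assumed mRS set): 1/20 = 5.0 points

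Two such changes at an assumed n = 30 take 14/30 = 46.7% (exact 95% CI 28.3 to 65.7) to 12/30 = 40.0% (22.7 to 59.4). A subject who leaves the denominator has a smaller effect. Removing one late death from 14/30 gives 14/29 = 48.3%, a shift of 1.6 points.

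**The case against.** The open window is deliberate, explained and disclosed, and the ±14-day result will be reported beside it. A reader might infer that the study will produce no genuine 90-day mRS result. The documents do not support that, because section 7.8 keeps one. A reader might also want the ±14-day analysis restored as the headline, but that would only swap the labels on two analyses already planned. It is a preference, not a correction.

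The listing in item 7 is also a safeguard, and in a study of up to 50 subjects late scores would be hard to hide. This stands only in part. Item 7 does not say whether the listing uses days 76 to 104 or its own open window, and on the second reading a day-180 score would not appear.

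A reader might infer that the SAP scores any death with a missing mRS as 6 whatever its date. That goes too far. Death must be the reason the score is missing, and a subject alive but unassessed through day 104 who died on day 120 could be classed as missing for another reason and excluded. The absence of a date leaves two readings open. It does not state the worse one.

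Finally, subject C does not come from the Covid-19 extension. The case arises under any window that opens before day 90, including the protocol's own, and the death still shows in item 6, which is also run in the mRS set. This is correct. It also means that the ±14-day analysis does not remove the contradiction: the death rule itself has to change.

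**Conclusion.** The point holds for the main mRS analysis and for the death rule. As written, a death by day 90 that follows a score of 2 or less on days 76 to 89 counts as independence. A death well after day 90 can be read as a 90-day mRS of 6. Scores have no last day. The mITT repeat and the carry-forward analysis in section 7.8 use the same day-76 lower limit, so they inherit the open window.

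The weight is modest. The endpoint is secondary, no hypothesis is tested, and few subjects are likely to be affected; the documents do not allow a count. The effect is 2.2 points per reclassified subject at n = 45, or 3.3 to 5.0 points on the assumption of 20 to 30 subjects in the mRS set. It is worth correcting because the remedy is cheap and the set was built for comparison with published 90-day results.

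**What to change.** In SAP 7.5.2 item 7, with matching text in sections 3 and 7.8:

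1. **Death rule.** Score mRS 6 for every death on or before day 90, regardless of any earlier score. Do not score later deaths as a 90-day mRS of 6; list them, as item 6 does. Apply the same rule in the ±14-day analysis. A cut-off at day 104 would not be enough, because deaths on days 91 to 104 would still disagree with item 6.
2. **Window.** Keep the Covid-19 extension but state its last day. Where a subject has several eligible scores, use the one closest to day 90. Tabulate the day of assessment.
3. **Consistency.** State in section 3 that item 7 is an exception to the rule on out-of-window measurements, and say which window the item 7 listing uses.

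The cost is a few sentences and a few lines of code. The dates of death and assessment are already needed for items 6 and 7. If the analysis has been run, a footnote and a rerun with the bounded rules would do. The downside is that a very late score, or a subject with no score who died after day 90, may leave the headline row.
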